PP-MI intervention. Participants randomized to PP-MI will receive a treatment manual. For each session, a PP exercise will be described in the manual, with instructions and space to write about the exercise and its effects. Next, an MI section will outline specific MI-based topics (e.g., pros/cons, managing slips) and facilitate physical activity goal-setting. Following randomization (in-person visit #2), interventionists will introduce PP exercise #1 and MI session #1 to participants to aid engagement. Following visit #2, participants will engage in weekly, 30-minute phone calls for the next 8 weeks. Participants will independently complete PP exercises and MI-based goals between phone sessions and review them during phone sessions over 8 weeks. PP and MI components will be delivered stepwise within sessions (rather than intertwined) based on our experience, participant feedback, and pilot work.

PP component details. The PP portion of phone sessions (15 mins) will be structured to include: (i) review of the prior PP exercise, (ii) discussion about how to translate the PP exercise skills to daily life (e.g., related to physical activity goals or other activities), including a specific focus on how such skills can be used to foster social support and interactions, and (iii) assignment of the next exercise via guided review of the treatment manual.

Session 1: Counting blessings ⁶¹	Participants recall three events, small or large, in the preceding week that were associated with satisfaction, happiness, pride, or other positive states
Session 2: Gratitude letter ²⁴	Participants write a letter of gratitude thanking a person for their support or kindness.
Session 3: Enjoyable and meaningful activities ⁶⁴	Participants complete three activities: an enjoyable activity alone, an enjoyable activity with another person, and a meaningful activity completed alone or with others.
Session 4: Implementation	Participants focus on implementing positive psychology skills into daily life.
Session 5: Recalling past success ⁶³	Participants recall an event in which they experienced success. They next write about the event, their contribution to the success, and positive feelings elicited by recalling it.
Session 6: Using personal strengths, part 1 ²⁴	Participants identify a signature strength, then find a specific new way to use that strength in the next 7 days.

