Session 7: Using personal strengths, part 2 ²⁴	Participants identify a second signature strength, then find a specific new way to use that strength in the next 7 days.
Session 8: Acts of kindness ⁶²	Participants complete three acts of kindness, planned or spontaneous, in a single day.
Session 9: Planning for the future	Participants review the positive psychology skills they learned in the program, then make a plan to use their skills in the future.

MI component of PP-MI. This will be adapted from our PP-MI program in ACS patients, [name] MI interventions,¹⁰⁻¹² and data from T2D patients. The MI portion of calls (15 mins) will assess participant motivation to increase physical activity (safe, specific activity goals will be obtained from their medical providers), and plan action steps or cognitive work to boost motivation. We will use established models of goal-setting and feedback based in social cognitive theory^{67,68} and the transtheoretical model of behavior change⁶⁹ that utilize setting of proximal, attainable, explicit goals and specific feedback to reinforce progress and enhance self-efficacy. We will typically focus on walking, as brisk walking is feasible as a first step in becoming active for T2D patients⁷⁰ and can improve health.⁷¹ The ultimate physical activity goal in nearly all cases will be moderate physical activity for ≥ 150 min/week, per ADA guidelines.⁴³ Gradual, safe physical activity progression will be ensured via a stepwise approach, symptom monitoring, and coordination with participants’ physicians. Participants will also be given a digital pedometer (Omron) that clips on a belt or other article of clothing, to promote and track physical activity. Finally, this enhanced MI program will also focus on reduction of sedentary time by helping participants to track sitting time and develop strategies to reduce such episodes,⁷²⁻⁷⁴ using the framework for increasing physical activity and our team’s experience with sedentary time interventions.⁷⁵ Participants will be mailed a graph of their weekly step counts two times over the course of the study. The graph updates will be sent at the middle and end of the study (i.e. following sessions 4 and 8).

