5A’s model (all sessions)	Interventionists: (a) Ask about progress on the prior cognitive (e.g., pros/cons of becoming active) or physical activity goal, (b) Advise about the benefits of physical activity on health and function, (c) Assess current stage of change and barriers/facilitators to change, (d) Assist with setting a goal, and (e) Arrange the next phone session.
Session-specific topics	Session 1: Introduction to MI tools and tracking of physical activity Session 2: Setting a SMART (Specific, Measurable, Attainable, Relevant, Time-based) activity goal Session 3: Identifying barriers and problem-solving around them Session 4: Using social and equipment resources Session 5: Finding new walking routes (neighborhood walkability audit) Session 6: Using neighborhood resources Session 7: Managing slips Session 8: Reducing sedentary time/taking breaks Session 9: Planning for the future

Walkability audit. Built environment audits (see attachment) can promote physical activity by helping participants find new opportunities for physical activity, manage environmental barriers, and change perceptions about their environment.^{76,77} PP-MI participants will complete the 15-item Microscale Audit of Pedestrian Streetscapes-Mini (MAPS-Mini),⁷⁸ a walkability audit that has participants identify walkways, parks, traffic, and other features in their neighborhood and usual walking routes by completing checklists as they explore these areas. Participants will be oriented to MAPS-Mini administration in session 5 and complete it in the

next week. Information from this audit will be used during MI sessions to facilitate the setting of practical physical activity goals based in participants' local areas.

Training and fidelity. All team interventionists have delivered PP-MI. Once the intervention is refined for T2D, they will receive additional training via didactics, role play, and supervised interviews. During the study, weekly interventionist supervision will be led by PI [name] (PP content) and [name] (MI). All sessions will be recorded; supervising study staff (Drs. [name], [name], [name], or [name]) will rate a random selection (20% at minimum) for fidelity using scales for the PP and MI components, respectively, and provide feedback.

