To measure physical activity, we will use the ActiGraph GT3X+ accelerometer,⁸² a small, silent device without readout that is worn at the hip and stores data for several weeks; it has been validated and used in many populations, including T2D, to measure habitual physical activity.⁸³ The GT3X+ is a half-dollar-sized device that is very lightweight, clips to a belt or

shoe, and has no sharp edges, shock risk, or visible readout (or any identifying data). Participants will wear the devices for 7 days. We will consider 5 valid days of wear (8+ hours per day) to be sufficient; participants will re-wear devices if needed. In a recently completed PP-MI study in ACS patients (n=128; PHS IRB# 2014P001756), we used these devices/methods with good results. Sedentary time will also be measured with Actigraphs, using protocols to differentiate between sedentary time and device non-wear.^{84,85} Data will be downloaded onto our study team's local computers without need to transmit data to external servers.

D. Procedures

A single venous blood sample will be collected at baseline and 8 weeks by study staff trained in phlebotomy, for A1C. No other procedures will be performed.

E. Data collected and when the data is to be collected (see Table 1, below)

Baseline characteristics. To allow us to better understand our study population (and to allow for limited/qualitative accounting for covariates, we will record subjects' baseline characteristics (age, gender, race/ethnicity, duration of diabetes diagnosis, medical and psychiatric comorbidities, medications, and baseline lipids, and hemoglobin A1c). Data will be obtained at the initial interview and supplemented with information from medical records.

Feasibility and acceptability (*Aim 1; # of PP-MI sessions completed, participant ratings of PP-MI ease and utility*). Interventionists will record completion of PP-MI sessions at each session (weeks 1-8). A completed PP-MI session requires both: (i) PP exercise completion and phone discussion, and (ii) the MI portion of the call must end with a specific physical activity-based goal for the next week. In addition, at intervention calls, participants will separately report ease and utility (0-10 scales) of the prior week's PP exercise and MI-based goal-setting, for 4 total ratings per session.

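### The primary feasibility threshold is 6 of 8 sessions in the hypotheses but 8 of 11 in the power analysis, and the protocol describes no 11-session programme

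*Combined protocol and SAP*

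**What the plan says.** **Threshold.** The hypotheses in section II expect a majority of the 30 PP-MI participants to complete 6 or more of 8 sessions. Section VI.D gives 80% power to show that the proportion completing 8 or more of 11 sessions exceeds 50%. It uses a planning rate of 75%, which it attributes to prior work and states for three-quarters of sessions.

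**Number of sessions.** Section III.B tells patients there are 8 weekly sessions. Section V.A says that at visit #2 "interventionists will introduce PP exercise #1 and MI session #1 to participants to aid engagement", and that after this visit "participants will engage in weekly, 30-minute phone calls for the next 8 weeks". Section V.E records completion in weeks 1-8. The PP and MI content tables in V.A each run to nine; the last MI entry is "Session 9: Planning for the future".

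**Measure and analysis.** In VI.A/B the Aim 1 statement refers to the percentage of phone sessions completed, but the measure listed beneath it is exercise completion. Section VI.C plans descriptive statistics for Aim 1. The test against 50%, with its alpha, is only in VI.D.

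**What a completed session is.** Section V.E requires the PP exercise to be done and discussed, and also that "the MI portion of the call must end with a specific physical activity-based goal for the next week". Section V.A lets the MI portion "plan action steps or cognitive work to boost motivation". Its 5A's row, which applies to all sessions, has the interventionist ask "about progress on the prior cognitive (e.g., pros/cons of becoming active) or physical activity goal".

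**The concern.** Feasibility is the primary aim, and its result is one proportion: how many of 30 participants are completers. Two sections of current text define a completer by different counts over different denominators, and one of those denominators does not exist in the programme as described. Someone analysing the trial from VI.D could not apply its rule without first choosing how to convert it. If that choice is made after the data are in, the claim that a majority completes the programme is open to challenge.

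Three smaller gaps bear on the same proportion. The nine listed sessions leave it unclear whether the in-person introduction counts. The measure in VI.A/B names exercises instead of sessions. The goal criterion in V.E can be read as narrower than the MI content that V.A allows.

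**Working it through.** **1. The plan's power figure.** Inputs from VI.D: n = 30, null 0.50, true proportion 0.75, two-sided alpha 0.05, binomial test.

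- Exact two-sided p-value at 20 of 30: 0.0987. At 21 of 30: 0.0428. So 21 completers are needed.
- Power = P(Bin(30, 0.75) ≥ 21) = 0.803.

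The stated 80% reproduces. The session threshold does not enter this formula, only the proportion of participants who are completers.

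**2. The two thresholds.**

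- Section II: 6/8 = 75.0%.
- Section VI.D: 8/11 = 72.7%.
- Three-quarters of 8 is 6, so the 75% planning rate matches section II exactly.
- Three-quarters of 11 is 8.25, which needs 9 sessions, so 8 of 11 falls just short of the level for which the rate is stated.

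**3. Session counts in the protocol.**

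| Place | Count |
|---|---|
| II, hypotheses | 8 |
| III.B, description to patients | 8 |
| V.A, weekly calls | 8 |
| V.E, completion recorded | weeks 1-8 |
| V.A, PP and MI content tables | 9 |
| VI.D, power analysis | 11 |

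Nine may be one in-person introduction plus eight calls. Nothing in the protocol gives eleven.

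**4. Can the rules disagree on one participant?**

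- As counts: a participant with 6 or 7 completed calls meets section II. That participant does not reach the 8 sessions in VI.D, which with eight calls means every call.
- As percentages of eight sessions: 0.727 × 8 = 5.8, so 6 are needed, the same as in section II.
- In an 11-session programme: 8 sessions meet VI.D but are below three-quarters.

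The rules therefore agree only after a conversion that the plan does not state.

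**5. Does the mismatch affect power?** Only if the 75% is tied to a particular rule. Assumption, not in the documents: equal per-session completion probability, with within-person correlation from 0 to 0.5 (beta-binomial).

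| What the 75% is tied to | Proportion under the other rule | Power for that proportion |
|---|---|---|
| 6 of 8 | 0.791 (corr. 0) to 0.753 (0.5) reach 8 of 11 | 92.0% to 81.5% |
| 8 of 11 | 0.712 (corr. 0) to 0.747 (0.5) reach 6 of 8 | 64.5% to 79.1% |

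In the second row, power is 73% at correlation 0.1, 76% at 0.2 and 78% at 0.3. With the 75% tied to 6 of 8 and the test applied to 6 of 8, power is 80.3%.

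**6. Description or test.** A bare majority of 30 is 16 or more; the test in VI.D needs 21 or more. Section VI.C, which plans only description, does not say which one decides the hypothesis.

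**7. The goal criterion.** The 5A's row sets a cognitive goal and a physical activity goal side by side. If a cognitive goal does not satisfy V.E, three such calls leave 8 − 3 = 5 completed sessions. A participant who took every call and did every PP exercise would then be a non-completer. The documents give no frequency for this.

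**The case against.** The strongest reply is that this is a slip in one line. Eight sessions or calls is the consistent figure everywhere except VI.D and the nine-row tables, the planning rate fits 6 of 8 exactly, and the power calculation does not use the session threshold. All of that stands, and it limits the finding to an inconsistency to be corrected.

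A reader might infer that the trial is underpowered, with power as low as 64.5%. The documents do not support this. That figure needs the 75% to be tied to 8 of 11, although VI.D states it for three-quarters of sessions. It also needs zero within-person correlation in completing sessions. Correlations of 0.1 to 0.5 give 73% to 79%, and VI.D itself uses 0.5 for ratings.

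A reader might also infer that V.E contradicts V.A on which calls count. That is too strong. The PP-MI description in V.A pairs MI topics such as pros and cons with setting activity goals. The example of a cognitive goal in the 5A's row concerns becoming active, so it could count as physical activity-based. At least one MI session, "Session 2: Setting a SMART" activity goal, is about such a goal directly. The strict rule may also be deliberate, since the control arm is described as lacking specific activity goal-setting. What remains is an ambiguity, because no section says how a cognitive goal is scored. The absence of a goal-type field is inferred from silence, as the session form is not reproduced.

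Finally, the exercise wording in VI.A/B may be loose phrasing: Table 1 speaks of exercise sessions. It is still the only listed Aim 1 measure, and it does not match the aim statement above it.

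**Conclusion.** The primary feasibility threshold is wrong as written in one of two places. Section II and VI.D differ (6 of 8 against 8 of 11; 75.0% against 72.7%), and 11 corresponds to nothing in the programme. Read as counts, the rules classify participants with 6 or 7 completed calls differently, so the primary conclusion depends on the rule chosen. How many participants this would affect cannot be derived from the documents.

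The 80% power stands: 80.3% for 30 participants, 75% against 50%, with 21 completers needed. It rests on the planning rate holding for the 6-of-8 rule, which is how VI.D words it. No loss of power is claimed from the threshold mismatch or from the goal criterion. The goal criterion is a secondary point that needs one clarifying sentence.

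**What to change.** 1. In VI.D, replace 8 of 11 with the 6 of 8 in section II. The power figure does not change.
2. In V.A or V.E, state whether the in-person introduction at visit #2 counts among the 8 sessions.
3. In VI.A/B, make the Aim 1 completion measure sessions completed as defined in V.E.
4. Carry the comparison with 50% from VI.D into VI.C, so that the rule deciding the primary hypothesis appears in the analysis section.
5. In V.E, state whether a cognitive goal about activity satisfies the second criterion for a completed session. The strict rule may stay.

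A goal-type field on the session form, a second rate for delivered sessions, and power at completer rates of 65-75% are optional. If the power range is wanted, it is 36% at 65%, 59% at 70%, 68% at 72% and 80% at 75%.

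Cost: items 1 to 5 are wording changes only, with no change to sample size, procedures or data collection.

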Positive psychological states and physical activity. In 164 patients with an acute coronary syndrome (ACS), we found that optimism 2 weeks post-ACS predicted greater 6-month physical activity (measured by accelerometer), controlling for baseline physical activity, medical factors, sociodemographics, depression, and anxiety ($\beta=102.5$; $p=.026$).³² We also completed a mixed methods project with ACS patients (N=32), finding that optimism and positive affect led to initiation of physical activity and predicted overall future health behavior adherence.^{33,34}

PP intervention studies in cardiac patients. We tested PP in two controlled trials in patients with heart disease. In a small pilot (N=28), PP was associated with more improvement in mental health outcomes than either attentional control or mindfulness interventions.²⁵ We then used the above qualitative interviews to refine the PP intervention and studied the revised intervention in 48 post-ACS patients. The intervention was well-accepted and led to improvements in psychological status (positive affect, depression, and anxiety), compared to usual care.³⁵ We are now examining the effects of PP on activity after ACS.

PP-MI intervention studies. In concert with [name], who has much experience testing MI in medical cohorts,¹⁰⁻¹² we have developed a combined PP-MI intervention that is now being studied in a trial (N=128) comparing PP and PP-MI for ACS patients with low physical activity.³⁶ In the first 50 participants, both conditions were associated with increases in physical activity. However, PP-MI participants had even greater physical activity improvement (12.6 metabolic equivalent [MET]-hours; effect size difference: $d=.33$) at 16 weeks, compared to PP. This data further supports the idea that PP, and especially PP-MI, can improve physical activity in medical populations.

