- For self-reported physical activity, we will use the IPAQ, well-validated in diverse settings.
- For self-reported smoking history, we will use the Cigarette Use Questionnaire.
- For self-reported alcohol use, we will use the Alcohol Use Disorder Identification Test – Consumption (AUDIT-C).

Medical outcomes (*Aim #3; exploratory*). At baseline and follow-up, we will also measure weight and A1C.

Table 1. Schedule of study events/assessments.

	Pre-enrollment	Enrollment	Weeks 1-8	Week 8	Week 16
Assessment for inclusion criteria (T2D, IPAQ)	X				
Assessment for exclusion criteria (e.g., cognitive screen, other medical conditions limiting activity)	X				
Interview and chart review for baseline characteristics		X			
Self-report measures		X		X	X
Vital signs (weight) and A1C*		X		X	
Accelerometer (MVPA and sedentary time)		X		X	X
PP-MI exercise sessions			X		
Session ratings by participants (ease/utility)			X		

*Will use values from clinical visit (or within 3 weeks in the case of A1C) if available.

VI. Biostatistical analyses:

A and B. Specific data variables and study endpoints

Specific Aim 1 (*feasibility and acceptability*): To determine whether the PP-MI intervention is feasible (assessed by % of total PP-MI phone sessions completed) and well-accepted (assessed by participant ratings of the ease and utility of each PP-MI session) among T2D patients with low baseline activity.

Measures:

- Rates of completion of exercises (recorded by study trainer)

Specific Aim 2 (physical activity): To assess whether PP-MI is associated with larger increases in MVPA, and less sedentary time, on accelerometer at 8 and 16 weeks, compared to MI.

Measures:

- MVPA in mean minutes per day
- Sedentary time in mean minutes per day

Specific Aim 3 (additional outcomes): To explore whether the PP-MI intervention is associated with greater improvements on other psychological, behavioral, and medical outcomes, compared to MI.

Measures:

- Psychological measures: PANAS, LOT-R, SEE, HADS, BRS, MSPSS
- Behavioral measures: SDSCA, % medication adherence, IPAQ, PF-20, PDI
- Medical outcomes: Weight, BMI, and A1C

C. Statistical methods

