All analyses will be performed under the direction of biostatistician [name]. All analyses will be performed using Stata 14.0. Alpha for between-group comparisons will be set at $p=.05$. We will use descriptive statistics (means, standard deviations, proportions for the Aim 1 feasibility/acceptability outcomes. For Aim 2, we will compare between-group improvement from baseline in mean minutes/day of MVPA (and sedentary time) at 8 weeks using a random effects regression model, with a random intercept for each patient, allowing us to include participants with some missing data.¹⁰¹ For Aim 3, we will likewise compare change from baseline on all measures (e.g., self-care, A1C) at 8 weeks, using random effects models. We will secondarily compare outcomes at 16 weeks, and will complete sensitivity analyses by sex. All variables used in minimization (age, gender, baseline MVPA, Charlson index) will be included as covariates in these models as per protocol using this method.⁶⁰ We will also measure pre-post effect size (Cohen's d , defined as change in the outcome measure divided by the standard deviation of the measure across all time points) of PP-MI for each Aim 2/3 outcome. If there are significant between-group differences in physical activity outcomes, we will use mediation analyses¹⁰² to evaluate a pathway from PP-MI to proximal targets (positive affect/optimism/self-efficacy) to physical activity.

D. Power analysis

For our primary aim (feasibility/acceptability), in our prior work, 75% of subjects completed three-quarters of sessions.^{25,35} Using the same rate, with 30 PP-MI participants we will have 80% power (two-sided $\alpha=0.05$, binomial proportion test) to demonstrate that the proportion who complete ≥ 8 of 11 PP-MI sessions is larger than 50% (i.e., a majority). Likewise, mean PP ease/utility scores were 7.8 \pm 1.8 in prior work;³⁵ with $n=30$ (and 4 weekly ratings per participant), we will have 93% power (using a within-person correlation of 0.5 for ratings across exercises) to detect a true mean score of >7.0 on composite ratings. This initial trial is not powered to definitively test group differences on physical activity and other Aim 2/3 outcomes, but it will allow us to gather data on PP-MI's impact on these outcomes at this key early stage.

VII. Risks and discomforts

A. Complications of surgical/non-surgical procedures

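### The Aim 1 measure listed in VI.A/B (completion of exercises) conflicts with the two-part definition of a completed PP-MI session in V.E, and the power statement rests on a rate borrowed from PP-only trials

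*Combined protocol and SAP*

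**What the plan says.** Five places in the protocol bear on how Aim 1 feasibility is scored.

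- **VI.A/B, Aim 1 sentence.** The intervention is to be judged "feasible (assessed by % of total PP-MI phone sessions completed"), with acceptability judged by the participants' ease and utility ratings.
- **VI.A/B, Aim 1 Measures.** The list under that sentence has one entry: "Rates of completion of exercises (recorded by study trainer").
- **V.E, Feasibility and acceptability.** "Interventionists will record completion of PP-MI sessions at each session (weeks 1-8"). The definition has two parts. The first is introduced as follows: "A completed PP-MI session requires both: (i) PP exercise completion and phone discussion". The second concerns how the call closes: "the MI portion of the call must end with a specific physical activity-based goal for the next week".
- **II, Hypotheses.** A majority of the 30 PP-MI participants are expected to complete at least 6 of 8 PP-MI sessions in full.
- **VI.D, Power analysis.** The planning rate is given as "in our prior work, 75% of subjects completed three-quarters of sessions", with two references. Then "with 30 PP-MI participants we will have 80% power" to show that the proportion completing at least 8 of 11 PP-MI sessions exceeds 50%.

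Section I.B describes the two referenced studies under its heading on PP interventions in cardiac patients: "We tested PP in two controlled trials in patients with heart disease". It mentions no MI component there and treats the PP-MI work in a separate paragraph.

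**The concern.** VI.A/B is where an analyst looks for the endpoint. Read literally, its Measures entry drops the phone discussion and the activity goal from the definition of completion. A week in which the exercise was done but no goal was set would count as complete. The headline feasibility figure could then describe uptake of the PP exercises and not of the combined programme, which is what the primary aim asks about.

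The gap between the two scorings need not be zero. In V.A, the MI part of the call may plan either action steps or cognitive work, and the 5A's row refers to a previous goal that may be cognitive or activity-based. A properly delivered call could therefore end in a cognitive goal and not meet part (ii) of V.E.

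The power statement adds a second question. Its 75% comes from trials of a programme with no described MI part, but it is applied to PP-MI sessions, which need one.

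**Working it through.** **1. Direction of the difference between the two scorings.** For each participant, let E be the number of weeks with the exercise completed and S the number of sessions complete under V.E. Every session counted in S has a completed exercise, so S ≤ E for everyone. The share of participants reaching any threshold is therefore at least as high under E as under S.

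Example with the 6-of-8 threshold from the Hypotheses: E = 7, and two of those seven calls end without an activity goal.
- Measures entry: 7 of 8, and 7 ≥ 6, so the participant passes.
- V.E: 7 − 2 = 5 of 8, and 5 < 6, so the participant fails.

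**2. The plan's own power figure.** Inputs from VI.D: n = 30, null proportion 0.50, assumed proportion 0.75, two-sided alpha 0.05, one-sample binomial test.
- Critical value: under p = 0.50, P(X ≥ 20) = 0.0494 and P(X ≥ 21) = 0.0214. The smallest count with an upper tail of at most 0.025 is 21.
- Power: P(X ≥ 21 | n = 30, p = 0.75) = 0.803.

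This reproduces the stated 80%. The normal approximation without continuity correction gives 0.816.

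**3. Dependence on the 75%.** The table uses the same test and the same critical value of 21. The true participant-level rates are assumptions, because the protocol gives no rate for the two-part definition.

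| True share reaching the threshold | P(X ≥ 21), n = 30 |
|---|---|
| 0.80 | 93.9% |
| 0.75 | 80.3% |
| 0.72 | 68.1% |
| 0.70 | 58.9% |
| 0.65 | 35.8% |
| 0.60 | 17.6% |

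**4. The session threshold.** Three-quarters of sessions is 6/8 = 0.75 in the Hypotheses; VI.D uses 8/11 = 0.727. The binomial power does not change if the participant-level rate stays at 75%, but the two thresholds define different endpoints.

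**The case against.** The strongest reply is that one loosely worded entry is out of line with everything around it. The sentence directly above it, the Hypotheses, V.E and VI.D all count PP-MI sessions. Table 1 labels the contacts as PP-MI exercise sessions, so exercises may simply be shorthand for sessions. Nothing says that the entry overrides V.E. This stands in part: the protocol does not settle on exercise-only scoring. It contradicts itself, and the contradiction lies in the section that names the endpoints.

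The ratings are not missing from the plan either. They appear in the Aim 1 sentence, V.E, Table 1 and VI.D. Only their line in the Measures list is absent.

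A reader might go further and infer that the 80% power is overstated, or that the 75% is a rate of exercise completion. The documents support neither. The 80% reproduces. VI.D describes the 75% in terms of sessions, and how the source trials counted a session is not stated. Nor does 80% require every call with a completed exercise to end in a goal; it requires only a two-part participant-level rate of 75%. For example, with independent sessions, a per-session rate of 0.779 gives a 75% chance of at least 6 of 8. An exercise rate of 0.82 with goals set in 95% of those calls gives 0.82 × 0.95 = 0.779. The population and programme differ from the source trials, so the true rate may be lower, equal or higher.

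Finally, VI.C plans only descriptive statistics for Aim 1, so the power figure decides little in this pilot. That is fair, and it is why the power caveat is secondary here.

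**Conclusion.** The Measures entry in VI.A/B is inconsistent with the Aim 1 sentence above it and with V.E. This is a contradiction in the scoring of the primary aim. If the entry were used, feasibility could be overstated and could not be understated. The direction follows from the definitions alone. The size depends on how often a call with a completed exercise ends without an activity goal, and the documents give no figure for that.

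The power statement contains no arithmetical error. Its 80% is conditional on a 75% rate borrowed from PP-only cardiac trials, and VI.D does not say so. At n = 30, an assumed true rate between 65% and 75% gives power between 35.8% and 80.3%; a rate above 75% gives more. The conclusion that the trial is underpowered for Aim 1 is not shown.

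**What to change.** In VI.A/B, replace the Aim 1 Measures entry with:

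1. the number of PP-MI sessions completed under the two-part V.E definition, scored for each participant against the 6-of-8 threshold in the Hypotheses, over all participants randomised to PP-MI;
2. the ease and utility ratings (four per session, as in V.E);
3. exercise completion, labelled as a descriptive component only.

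Reconcile the 8-of-11 threshold in VI.D with the 6-of-8 threshold, so that one rule applies throughout.

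Optionally, state in VI.D that 75% is a session-completion rate from PP-only trials, that the 80% power is conditional on it, and what the power would be at lower rates (58.9% at 70%, 35.8% at 65%).

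The cost is a change of wording. Session completion and ratings are already recorded at each call, and the sample size stays the same. The downside is a possibly lower reported completion rate and a less favourable power statement.
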